## **5.0 METHODOLOGY**

#### 5.1 Entry Criteria

#### 5.1.1 **Diagnosis/Condition for Entry into the Trial**

Male and female patients with TNM clinical stage III, IVA, or IVB squamous cell carcinoma of oral cavity (excluding lip), oropharynx, hypopharynx, and larynx eligible for curative-intent treatment. A total of 57 patients will be enrolled with 34 of those patients being HPV-positive and 23 patients being HPV-negative. Enrollment to each sub-category will end when the target is met.

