Safety: All Subjects as Treated (ASaT)Primary Endpoint(s)1) Safety and Tolerability 2) Efficacy: Complete Response (CR) Rate at treatment end.Statistical Methods for Key Efficacy AnalysesThe key efficacy analysis is estimation of the treatment end CR rate using Exact method based on binomial distribution. There is no statistical Methods for Key Safety AnalysesStatistical Methods for Key Safety AnalysesCount and percentage of AE will be provided. Fisher's exact test will be used to compare the proportions.Interim AnalysesInterim efficacy analysis will be performed when 27 subjects have enrolled in this study and are evaluable for response (day 150). Efficacy results will be reviewed by the DSMB.MultiplicityNot included in this study.Sample Size and PowerSample size is based off the efficacy endpoint. It is estimated that57 evaluable patients, will be		
Primary Endpoint(s)1) Safety and Tolerability 2) Efficacy: Complete Response (CR) Rate at treatment end.Statistical Methods for Key Efficacy AnalysesThe key efficacy analysis is estimation of the treatment end CR rate using Exact method based on binomial distribution. There is no statistical hypothesis.Statistical Methods for Key Safety AnalysesCount and percentage of AE will be provided. Fisher's exact test will be used to compare the proportions.Interim AnalysesInterim efficacy analysis will be performed when 27 subjects have enrolled in this study and are evaluable for response (day 150). Efficacy results will be reviewed by the DSMB.MultiplicityNot included in this study.Sample Size and PowerSample size is based off the efficacy endpoint. It is estimated that57 evaluable patients, will be	Analysis Populations	Efficacy: Full Analysis Set (FAS)
2) Efficacy: Complete Response (CR) Rate at treatment end.Statistical Methods for Key Efficacy AnalysesThe key efficacy analysis is estimation of the treatment end CR rate using Exact method based on binomial distribution. There is no statistical hypothesis.Statistical Methods for Key Safety AnalysesCount and percentage of AE will be provided. Fisher's exact test will be used to compare the proportions.Interim AnalysesInterim efficacy analysis will be performed when 27 subjects have enrolled in this study and are evaluable for response (day 150). Efficacy results will be reviewed by the DSMB.MultiplicitySample Size and PowerSample size is based off the efficacy endpoint. It is estimated that57 evaluable patients, will be		Safety: All Subjects as Treated (ASaT)

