Statistical Methods for Key Efficacy AnalysesThe key efficacy analysis is estimation of the treatment end CR rate using Exact method based on binomial distribution. There is no statistical hypothesis.Statistical Methods for Key Safety AnalysesCount and percentage of AE will be provided. Fisher's exact test will be used to compare the proportions.Interim AnalysesInterim efficacy analysis will be performed when 27 subjects have enrolled in this study and are evaluable for response (day 150). Efficacy results will be reviewed by the DSMB.MultiplicityNot included in this study.Sample Size and PowerSample size is based off the efficacy endpoint. It is estimated that57 evaluable patients, will be	Primary Endpoint(s)	1) Safety and Tolerability
Statistical Methods for Key Efficacy AnalysesThe key efficacy analysis is estimation of the treatment end CR rate using Exact method based on binomial distribution. There is no statistical hypothesis.Statistical Methods for Key Safety AnalysesCount and percentage of AE will be provided. Fisher's exact test will be used to compare the proportions.Interim AnalysesInterim efficacy analysis will be performed when 27 subjects have enrolled in this study and are evaluable for response (day 150). Efficacy results will be reviewed by the DSMB.MultiplicitySample Size and PowerSample size is based off the efficacy endpoint. It is estimated that57 evaluable patients, will be		2) Efficacy: Complete Response (CR) Rate at
treatment end CR rate using Exact method based on binomial distribution. There is no statistical hypothesis.Statistical Methods for Key Safety AnalysesCount and percentage of AE will be provided. Fisher's exact test will be used to compare the proportions.Interim AnalysesInterim efficacy analysis will be performed when 27 subjects have enrolled in this study and are evaluable for response (day 150). Efficacy results will be reviewed by the DSMB.MultiplicityNot included in this study.Sample Size and PowerSample size is based off the efficacy endpoint. It is estimated that57 evaluable patients, will be		treatment end.

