is estimated that57 evaluable patients, will be	Sample Size and Power	Sample size is based off the efficacy endpoint. It
	1	
		sufficient to determine the efficacy endpoint
with a power $= 0.8$ and one-sided alpha $= .05$ .		

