#### 8.4.3 Statistical Methods

#### 8.4.3.1 Statistical Methods for Efficacy Analyses

The efficacy endpoints, analysis population, and statistical methods (including missing data handling) that will be employed for the efficacy analyses are presented in Table 7.

The primary endpoint is the total CR rate (composite outcome of rCR, PET NPV, and pCR) on all subjects. We have designed the study to test the hypothesis that the CR rate will be greater than 40.2% assuming a rate of 60.4%. To test this, we will use a one sample, one-sided asymptotic equality test with the null hypothesis that the total CR rate will be 40.2%. This test will result in a p-value greater than 0.05 if fewer than 21 patients respond to treatment. Secondary endpoints will include rCR, pCR, PET NPV, PFS, OS, LRC, and DM rates. For the secondary endpoints, we will only estimate confidence intervals to understand the possible range of values rather than doing formal hypothesis testing. Survival curves for PFS and OS will be constructed using the Kaplan-Meier method and 1 and 2-year survival estimates will be calculated.

Endpoint Statistical Method		Analysis Population	Missing data approach			
rCR Rate	Exact binomial method: Clopper-Pearson 95% confidence interval	FAS	Subjects with missing data are considered non-responders			
pCR Rate	Exact binomial method: Clopper-Pearson 95% confidence interval	FAS 	Subjects with missing data are considered non-responders			
CR Rate	One sample, one-sided asymptotic binomial test	FAS	Subjects with missing data are considered non-responders			
Objective Response Rate (CR + PR)	Exact binomial method: Clopper-Pearson 95% confidence interval	FAS	Subjects with missing data are considered non-responders			
PFS (RECIST 1.1) by independent radiology review	Summary statistics using Kaplan-Meier method	ASaT	Censored at last assessment date			
OS	Summary statistics using Kaplan-Meier method	ASaT	Censored at last assessment date			
LRC rate	Exact binomial method: Clopper-Pearson 95% confidence interval	FAS	Subjects with missing data are considered as disease not under control			
DM rate Exact binomial method: Clopper-Pearson 95% confidence interval		FAS	Subjects with missing data are considered as disease not under control			

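### The plan gives three incompatible accounts of the primary CR analysis; one exact test should be named, because an asymptotic test exceeds 5% at some analysed counts just below plan

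*Combined protocol and SAP*

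**What the plan says.** The primary efficacy analysis is described in three places.

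- **8.1 summary table.** The key efficacy analysis is "estimation of the treatment end CR rate using Exact method based on binomial distribution. There is no statistical hypothesis". The sample-size row of the same table gives 57 evaluable patients, power 0.8 and one-sided alpha .05.
- **8.4.3.1 and Table 7.** The test covers all subjects: "We have designed the study to test the hypothesis that the CR rate will be greater than 40.2% assuming a rate of 60.4" per cent. The method is "One sample, one-sided asymptotic binomial test" in the Full Analysis Set (FAS). The text adds: "This test will result in a p-value greater than 0.05 if fewer than 21 patients respond to treatment".
- **8.4.7.3.** The original two-stage rule (13/27, then 21/39, null 40.2%) is followed by one-arm binomial rules by cohort. HPV+ rejects at 31 of 34 (null 74%, alternative 90%). HPV- rejects at 18 of 23 (null 50%, alternative 75%). Each is stated to have type I error 0.05 and power 80%.

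On the number analysed, 5.1.1 says "Enrollment to each sub-category will end when the target is met", whereas 8.4.7.1 continues accrual until 34 and 23 patients can be assessed for response. The FAS (8.4.2.2) requires completed treatment-end imaging.

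**The concern.** An analysis with no hypothesis cannot have a power or an alpha, so 8.1 contradicts itself as well as 8.4.3.1. A statistician following 8.1 would report an estimate with an interval. One following Table 7 would report an asymptotic p-value against 40.2%. One following 8.4.7.3 would apply two cohort cut-offs. This is an open-label, single-arm trial whose result is meant to inform a phase III decision, so the method should not be left to be chosen once the CR count is known.

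The choice of an asymptotic method also matters in itself. With small samples and a discrete outcome, the normal approximation can reject with one CR fewer than an exact test would need, which takes the true error above the stated 5%. Whether that happens depends on the exact number analysed.

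**Working it through.** **1. The plan's own figure.** For the two-stage rule, P(reject) = Σ over x = 14 to 27 of P(X₁ = x | 27, p) × P(X₂ ≥ 21 − x | 12, p). At p = 0.402 this is 0.0498, and at p = 0.604 it is 0.801. The stated 0.05 and 0.80 reproduce. The 21-responder threshold in 8.4.3.1 belongs to n = 39: z = (21/39 − 0.402)/√(0.402 × 0.598/39) = 1.74, p = 0.041, while 20/39 gives p = 0.079. It does not carry over to 57, since 21/57 = 36.8% is below the null.

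**2. Method.** The plan does not define the asymptotic variance. I take the uncorrected score test, which rejects at the smallest c with (c − n·p0)/√(n·p0·(1 − p0)) ≥ 1.645. Its true size is P(X ≥ c | n, p0) from the binomial. The exact test uses the smallest c for which that probability is at most 0.05. Power is P(X ≥ c | n, p1).

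**3. At the planned counts.** Both methods give the same cut-off.

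| Set | n | p0 | Cut (both) | Size | Power at p1 |
|---|---|---|---|---|---|
| All subjects (no interim stop) | 57 | 0.402 | 30 | 0.0387 | 0.908 (0.604) |
| HPV+ | 34 | 0.74 | 30 | 0.0375 | 0.750 (0.90) |
| HPV- | 23 | 0.50 | 16 | 0.0466 | 0.804 (0.75) |

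**4. Just below plan.** The plan gives no non-evaluable fraction. I assume 0 to 3 missing per cohort and 0 to 7 overall. Example, HPV- n = 22: n·p0 = 11 and √5.5 = 2.345. So 15 CRs give z = 4/2.345 = 1.71 (reject) and 14 give 1.28 (do not). P(X ≥ 15 | 22, 0.5) = 0.0669. The exact test needs 16.

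| Set | n | Score cut, size | Exact cut, size | Power, score → exact |
|---|---|---|---|---|
| HPV- | 22 | 15, 0.0669 | 16, 0.0262 | 0.84 → 0.70 |
| HPV- | 20 | 14, 0.0577 | 15, 0.0207 | 0.79 → 0.62 |
| HPV+ | 32 | 28, 0.0547 | 29, 0.0189 | 0.79 → 0.60 |
| HPV+ | 31 | 27, 0.0657 | 28, 0.0233 | 0.81 → 0.62 |
| All subjects (no interim stop) | 56 | 29, 0.0524 | 30, 0.0294 | 0.93 → 0.88 |

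For all subjects, the score test also exceeds 5% at n = 54 (0.0551), 52 (0.0579) and 50 (0.0608). It does not at 55 (0.0405), 53 (0.0425) or 51 (0.0445). In the cohorts there is no excess at HPV- 21 (0.0392) or HPV+ 33 (0.0454).

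**5. Sensitivity to what the plan leaves open.**
- If the 13/27 futility stop is binding, the all-subjects size is 0.028 to 0.044 at every n from 50 to 57.
- With a continuity correction, size is below 5% at all these counts.
- With the Wald (observed-variance) form, the HPV+ cut at n = 34 becomes 29 and the size 0.0909. This is the only variant that exceeds 5% at a planned count.

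**6. The written cohort cut-offs.** P(X ≥ 31 | 34, 0.74) = 0.012 and P(X ≥ 18 | 23, 0.5) = 0.005. Power at the stated alternatives is 0.554 and 0.468. These cut-offs match neither method at 5%, which would cut at 30 and 16.

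**The case against.** The strongest objection is that the error-rate excess is conditional several times over.

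- **Which test.** The asymptotic test is written only for all subjects against 40.2%. Applying it to the cohorts is an inference from Table 7, which names no other CR test, and from section 3.1, which states the CR hypotheses by HPV status. The cohort cut-offs actually written are conservative.
- **Which count.** Section 8.4.7.1 and the 8.1 table speak of evaluable patients, 5.10 replaces some dropouts, and 8.4.2.2 keeps patients resected before imaging. Table 7 also counts missing data as non-response. Against that, 5.1.1 closes each cohort at its enrolment target, 5.10 does not replace those who leave for adverse events or progression, and a patient without imaging is outside the FAS before the missing-data rule can apply. The documents conflict, so a shortfall is possible but cannot be sized from them.
- **Which variance and which stop.** A continuity correction or a binding stop removes the excess shown for the test that each affects. Section 8.4.7.3 writes 13/27 as a stop, while 8.4.7 leaves continuation to the DSMB.

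All of this stands, and it limits the error-rate part to some counts under some readings. It does not touch the contradiction.

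A reader might infer that the primary test generally runs above 5%. The documents do not support that: under the score test, size is below 5% at 57, 34 and 23 and at about half of the counts just below. A reader might also infer that the plan's two methods can give opposite test results. Section 8.1 describes exact estimation and offers no competing exact test. The one-CR difference is between the asymptotic test and the exact test proposed here.

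**Conclusion.** The contradiction stands without assumptions: 8.1 denies a hypothesis while stating power and alpha, 8.4.3.1 and Table 7 test 40.2% on all subjects asymptotically, 8.4.7.3 tests the cohorts, and no text ranks them.

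The error-rate consequence is narrower. It assumes an uncorrected score test and an analysed number a few below plan. Then size exceeds 5% at some counts, by at most about 1.7 percentage points (HPV- n = 22). For the all-subjects test the largest excess in the range examined is 1.1 points (n = 50), and it is nil if the 13/27 stop is binding. The cohort figures also assume that Table 7's test applies to the cohorts. Because an exact test has the same cut-offs at the planned counts and holds 5% at every count, there is no good reason to keep the approximation.

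**What to change.** In 8.1, 8.4.3.1 and Table 7:

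1. State which CR hypotheses are retained (all subjects, HPV+, HPV-). For each, name a one-sided exact binomial test at 5%, with the cut-off computed for the number analysed, and report a Clopper-Pearson interval. Table 7 already uses that interval for the other response rates.
2. Delete the sentence in 8.1 that denies a statistical hypothesis.
3. State how this rule relates to the all-subjects 40.2% test and its 21-responder threshold, which belongs to n = 39, and to the written 31/34 and 18/23 cut-offs. An exact 5% rule would cut at 30/34 and 16/23.
4. Reconcile 5.1.1 with 8.4.7.1 on whether the targets count enrolled or evaluable patients.

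Most of this is wording, but items 1 and 3 settle the primary hypotheses and so need an amendment under 8.2. The exact test costs nothing relative to the score test at 57, 34 and 23. At the affected counts it requires one more CR, and power at the stated alternatives falls, for example from 0.84 to 0.70 at HPV- n = 22 and from 0.81 to 0.62 at HPV+ n = 31.

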#### 7.1.2.6 **Tumor Imaging and Assessment of Disease**

#### 7.1.2.6.1 Baseline Tumor Imaging

Initial tumor imaging must be performed within 42 days prior to enrollment. Baseline imaging does not need to have a centralized study review to determine subject eligibility. The baseline imaging scan should be reviewed by each individual site prior to enrollment to confirm measurable disease.

Scans performed as part of routine clinical management are acceptable for use as the screening scan if they are of diagnostic quality and performed within 42 days prior to the enrollment.

The only required imaging modality for the study is a diagnostic quality CT scan of the neck. This should be adequate to fully include the primary tumor and involved locoregional disease. Additional imaging is allowed, but not required for the study. This includes, but is not limited to CT imaging of the head, chest, abdomen, and pelvis, MRI imaging, and FDG-PET imaging.

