#### 7.1.2.6.2 Tumor Imaging During Trial

The first imaging assessment should be performed at approximately **100 days after completion of radiation therapy**. For the purposes of this study, this is considered the "treatment end" imaging study. This will be approximately day 150 from the first dose of radiation. Due to treatment variations and delays, this may be delayed by up to 14 days.

Follow-up imaging will occur at scheduled intervals outlined on the Flow Chart. At 1 year following completion of the study treatment PET/CT imaging is not required, but is suggested

and is allowed so long as diagnostic quality CT images are included. Diagnostic quality imaging of the primary tumor site (CT scan of the neck) should be performed annually thereafter for up to 5 years. Images will be reviewed by the central radiologist at the end of the study to confirm disease response for purposes of study evaluation.

Additional imaging should be performed per clinical guidelines and is not required the study. Patients with clinical signs and symptoms of progression should have follow-up imaging as deemed clinically necessary. If this occurs during the study period, it should be reported to the study.

During the follow up period, if an instance occurs where the participants insurance will not approve a diagnostic CT scan a clinical evaluation will be used. No protocol deviation is needed but the insurance denial must be documented on the tumor assessment source documents.

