# 7.1.2.6.3 Assessment of Disease – RECIST 1.1, irRECIST 1.1, PET Response, Salvage Surgery

#### 7.1.2.6.3.1 RECIST 1.1

RECIST 1.1 will be applied by the individual sites for assessment of tumor response. Sites should also assess tumor response and progression per modified RECIST 1.1 and this data will be collected in the clinical database. Site assessment of tumor response and progression will be used for all patient decision making in the trial. See Section 11.3 and 11.4.

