#### 7.1.2.6.3.4 Salvage Surgery

Patients with residual disease considered resectable after all their planned therapy is completed may undergo a salvage surgical procedure, if that procedure is conceived as potentially curative.

PET imaging can be used to guide post treatment surgical need. The preference of the study would be to recommend no further therapy for any PET tumor avidity (CMR). However, this is not a requirement and will be left up to the discretion of the treating surgical oncologist.

Patients achieving a complete response who had advanced (N2 or greater) neck disease at presentation should be considered for an elective neck dissection after completion of all of their planned therapy if the post therapy imaging or clinical exam indicates persistent disease, despite RECIST 1.1 response. The nature of the neck dissection will be at the discretion of the treating head and neck surgeon.

Pathologic response to therapy will be evaluated following surgery. Pathological complete response (pCR) is defined as the absence of residual invasive and in situ cancer on hematoxylin and eosin evaluation of the completely resected sites of residual disease. Subjects who have a pathologic CR, but do not have a RECIST 1.1 CR will be included in the final efficacy analysis. This analysis will include the composite outcome of patients with RECIST 1.1 CR, Hopkins Criteria NPV (see section 11.5), and pathologic CR.

Patients who show signs of clear, clinical progression prior to the treatment end imaging may be considered for surgery. This will be at the discretion of the treating providers, including the surgeon, medical oncologist, and radiation oncologist. Patients who undergo surgery will be determined to have PD in terms of analysis of the primary endpoint.

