#### 8.4 Analysis Endpoints

#### 8.4.1 **Efficacy Endpoints**

Radiographic Complete response (rCR) rate: proportion of subjects in the analysis population who have a complete response on RECIST 1.1 imaging at treatment end.

PET NPV rate: proportion of subjects in the analysis population who are considered to have NPV based on Hopkins Criteria scoring at treatment end.

Pathologic complete response (pCR) rate: proportion of subjects in the analysis population who have stable disease (SD) or partial response (PR) on RECIST 1.1 imaging at treatment end, who undergo salvage surgical resection and have a complete response determined on histologic evaluation.

Overall Complete Response (CR) rate: this is a composite proportion of subjects in the analysis population with a rCR, PET NPV, and pCR. This is the primary measure of efficacy for the study.

Overall Response Rate (ORR): proportion of subjects in the analysis population who have complete response (CR) or partial response (PR) based on RECIST 1.1 imaging at treatment end.

Progression-Free Survival (PFS): time from Day -7 treatment administration to the first documented disease progression or death.

Overall Survival (OS): time from Day -7 treatment administration to death due to any cause.

Locoregional Control (LRC): time from day -7 treatment to date of local or regional relapse within the primary radiation treatment field (relapse in the head or neck region, excluding CNS recurrence).

Rate of Distant Metastases (DM): proportion of subjects in the analysis population who develop distant recurrence, as defined by recurrence outside of the primary radiation treatment field (head and neck region).

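### Section 8.4.1 and the PFS row of Table 7 disagree on what counts as progression, so 1- and 2-year PFS may be overstated

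*Combined protocol and SAP*

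**What the plan says.** Section 8.4.1 defines PFS as "time from Day -7 treatment administration to the first documented disease progression or death". It names no assessor and no imaging method.

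The efficacy-methods table (Table 7, Section 8.4.3) lists the endpoint as "PFS (RECIST 1.1) by independent radiology review", analysed in the All Subjects as Treated population. The entry in its missing-data column is "Censored at last assessment date". The accompanying text states: "Survival curves for PFS and OS will be constructed using the Kaplan-Meier method and 1 and 2-year survival estimates will be calculated". There is no formal test of PFS.

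Other sections determine how progression comes to light:

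- Section 7.1.2.6.2: in follow-up, if a participant's insurer "will not approve a diagnostic CT scan a clinical evaluation will be used". The same section has images read by the central radiologist at the end of the study.
- Section 6.3 flow chart: neck CT is marked at follow-up visits 1, 2, 3 and 5 to 8. Visit 4 has a directed physical examination and no CT mark.
- Section 7.1.2.6.3.4: "Patients who show signs of clear, clinical progression prior to the treatment end imaging may be considered for surgery". Patients so treated are PD for the primary endpoint.
- Section 8.4.2.2: patients resected before treatment-end imaging are in the efficacy analysis as PD. No PFS event date is given.
- Section 7.1.2.6.1: "The only required imaging modality for the study is a diagnostic quality CT scan of the neck". Other imaging is allowed.
- Section 7.1.2.6.3.1: "Site assessment of tumor response and progression will be used for all patient decision making in the trial".

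**The concern.** The definition and the analysis row describe different endpoints, and nothing reconciles them. A patient whose progression is established by examination, or at surgery without a prior scan, meets 8.4.1 on that date. The same patient does not meet the Table 7 label, because there is no image for an independent radiologist to read.

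If the table is followed to the letter, the patient is censored at the last assessment. The reason for censoring would then be the progression itself. That is informative censoring, and Kaplan-Meier estimates are biased upward under it.

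PFS is secondary and unpowered, but it is not purely descriptive. Section 4.2.3.1 says the survival endpoints will be compared with historical data and may be weighed in deciding whether to take the combination further. The trial has one arm, so no concurrent control shares the bias.

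**Working it through.** The documents give no PFS rate, event count or power for PFS, so there is no planned figure to reproduce. The check has two parts.

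**Timing.** The flow chart chains the visits from Day 150: visit 1 at 150 + 90 = 240, visit 2 at 240 + 90 = 330, visit 3 at 330 + 180 = 510, visit 4 at 510 + 180 = 690, visit 5 at 690 + 180 = 870. PFS runs from Day -7, so two years falls at about 730 - 7 = day 723. Neck CT is scheduled at about days 510 and 870. The last scheduled disease check before the 2-year estimate is therefore the visit 4 examination.

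**Direction and size (illustration).** All inputs below are assumptions, because the documents give none of them:

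- true 2-year PFS S: 60%, 70% or 80%, with exponential event times;
- share q of first PFS events that are progressions rather than deaths: 85%;
- share u of progressions with no reviewable image: 10%, 20% or 40%;
- median survival after progression: 12 months.

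If uncaptured progressions are censored when they occur, the event hazard falls by the factor 1 - uq, so S_obs = S^(1 - uq). For S = 0.70 and u = 0.20: 0.70^(1 - 0.20 × 0.85) = 0.70^0.83 = 0.744. For u = 0.10: 0.70^0.915 = 0.722.

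Two readings of Table 7 were then simulated with 200,000 subjects each. In reading (a) the patient is censored at the last scheduled scan and later death is ignored. In reading (b) progression is not counted but a later death is.

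| True 2-year PFS | Reading | u = 10% | u = 20% | u = 40% |
|---|---|---|---|---|
| 60% | (a) | 62.5% | 65.0% | 70.7% |
| 60% | (b) | 61.8% | 63.5% | 67.1% |
| 70% | (a) | 72.1% | 74.0% | 78.7% |
| 70% | (b) | 71.2% | 72.8% | 75.2% |
| 80% | (a) | 81.4% | 82.9% | 86.1% |
| 80% | (b) | 81.1% | 82.0% | 83.6% |

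The excess is about 1 to 2.5 points at 10%, 2 to 5 at 20% and 4 to 11 at 40%. With u = 0 it is zero.

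In patient numbers, a true 2-year PFS of 70% with 57 patients means about 57 × 0.30 = 17.1 first events by two years, if nobody is censored earlier. Of these, 17.1 × 0.85 = 14.5 are progressions. Losing 10% to 20% of them is 1.5 to 2.9 patients. For comparison, the sampling error at 70% is √(0.70 × 0.30 / 57) = 0.061, a 95% half-width of about 12 points.

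**The case against.** The two passages can be read together: 8.4.1 supplies the event and Table 7 the assessor of imaging. The censoring entry stands in a missing-data column and is repeated for OS, so it looks like a generic entry, not a decision to discard documented progression. That is fair. What the text shows is silence on these cases, not a rule that censors them.

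A reader might go further and infer that real progressors are lost from PFS and that the estimate is therefore wrong. The documents do not support that:

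- Death remains a PFS event, and Section 7.1.5.6 follows survival after progression. An uncaptured progressor can still become a later event.
- Section 8.4.2.2 sets early-resected patients to PD in the efficacy analysis. Section 7.1.2.6.3.4 is narrower and the PFS population is different, so their PFS handling is unclear, not plainly censoring.
- Imaging outside the neck is allowed, imaging is advised when progression is suspected, and nothing bars those scans from central review. Distant disease seen on a chest CT fits Table 7.
- A site call that the central reader rejects may be a false positive. Survival follow-up begins at confirmed progression or new therapy, and Section 11.4 provides for a repeat scan to confirm PD.

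It is also right that independent review protects an open-label, single-arm trial against site bias. Replacing it with site judgement as the main PFS analysis would exchange one bias for another.

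After all this, progression without a reviewable image still has no event rule or date.

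**Conclusion.** The inconsistency is real and should be resolved before PFS is analysed. Under a literal reading of Table 7 the error can only go upward, because documented progressions are removed or dated late. Counting later deaths reduces the error but does not remove it.

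The size is not known. About 1 to 5 points on 2-year PFS is an illustration for 10% to 20% uncaptured, and rests on the assumed event mix, exponential times and post-progression survival above. The 40% column shows sensitivity and is not a forecast. A bias of 1 to 5 points is smaller than the sampling uncertainty with 57 patients, but a wider interval does not correct a systematic shift against a historical benchmark.

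The primary CR analysis is not affected. This is a moderate point about a secondary endpoint.

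**What to change.** Reconcile the PFS row of Table 7 with Section 8.4.1:

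1. State that these are PFS events: documented clinical or pathologic progression (including progression found at a clinical evaluation that replaces a refused CT), surgery for progression before treatment-end imaging, documented distant metastasis, and death.
2. Give a date rule for each, such as the date of the examination, pathology report, operation or scan that first documents it.
3. Keep independent radiology review for progression that rests on imaging.
4. Report a PFS counting all documented progressions, including RECIST progression called by the site, beside the independent-review PFS, so that the gap is visible in any historical comparison.

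The cost is SAP wording and one extra analysis, with no change to patient procedures. Some events would rest on unblinded site judgement, and the reported PFS may be lower.
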